## **9 STATISTICAL CONSIDERATIONS**

Statistical analyses will be descriptive. Summary statistics will consist of sample size (N), means, standard deviations, medians, and minimum and maximum values for continuous variables, and counts and percentages for categorical variables. Tables will summarize all safety and efficacy outcome measures by actual treatment received. Summary tables will indicate the number of subjects with complete data for each measurement, event or outcome. No substitutions will be made for missing data. All analyses will be based on available data.

A detailed Statistical Analysis Plan will be written prior to data analysis. Significant deviations from the original statistical analysis plan will be detailed in the final study report.

This study intentionally is not powered and will enrolled 30 patients with 15 in each of the two randomization arms.

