#### **3.2 Secondary**

To assess the efficacy of human allogeneic MSCs administered intravenously—3 times at monthly

intervals—to subjects with advanced HF who underwent implantation of LVAD : Specifically, effect on 1) right (RV) and left ventricular (LV) structure and function, 2) inflammatory and cardiac biomarkers, and 3) clinical status.

[figure not shown]

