## 4 STUDY DESIGN

### 4.1 Description of the Study

This is a Phase IIa, double blind, placebo-controlled, multi-center, randomized study in subjects with advanced HF who are supported by LVADs.

The study will enroll 30 subjects and will consist of 2 cohorts. Enrolled subjects will be stratified by LVAD device type (HeartWare HVAD, HeartMate II or HeartMate III) and randomized at 1:1 into an experimental group (n=15) or a placebo group (n=15), respectively. Subjects in the experimental group will receive 1.5 million cells per kg, and subjects in the placebo group will receive 1.5 mL/kg Lactated Ringer's Solution at baseline, 1 month and 2 months.

All study participants will receive the MSCs or placebo within  $\pm 7$  days of the specified timing.

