## 4.2 Endpoints

### PRIMARY ENDPOINT

#### **Safety of MSCs assessed at the following time-intervals:**

Baseline and days 30, 60, 90, 180, and 360 post-initial infusion

1. Procedural complications
2. Vital signs
  - a. Temperature
  - b. Mean arterial blood pressure
  - c. Heart rate
  - d. Respiratory rate
  - e. Weight
  - f. LVAD parameters: Pump speed, flow, pulsatility and power
3. Uncontrolled systemic infection.
4. Hemodynamically unstable clinical arrhythmias that require appropriate defibrillator shock, anti-tachycardia pacing or initiation or escalation of antiarrhythmic medications.
5. Laboratory tests
  - a. Complete blood count (CBC)/ differential.
  - b. Comprehensive Metabolic Panel: Sodium, potassium, chloride, bicarbonate, blood urea nitrogen (BUN), creatinine, glucose, calcium, magnesium and liver function tests (ALT, AST, alkaline phosphatase, bilirubin and albumin)
  - c. Troponin-I.
  - d. Allosensitization (change in antibodies against HLA (panel reactive antibody test) from baseline for strong HLA antibody specificities (MFI>2000))
6. Electrocardiogram.
7. All-cause mortality. This will be reviewed by the DSMB. The LVAD population is a high risk group with very

high mortality, which will be taken into account when reviewing safety. Survival rate among HF patients with LVAD is 95% at 1 month, 81% at 1 year, 70% at 2 years, 59% at 3 years and 49% at 4 years. For patients enrolled within our study window, we would expect a 20% mortality rate in our patient population.

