## **SECONDARY ENDPOINT**

All secondary end points will be assessed pre-MSC infusion at days 0, 30, and 60, and also at days 90, 180, and 360. In addition, blood will be drawn 1 week after each infusion for potential biomarker analysis, depending on analysis of pre-infusion data. These 1-week post infusion blood samples will be frozen and stored.

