#### 2. NK cell depletion, defined as % reduction in NK cells from baseline to day 90.

## **EXPLORATORY ENDPOINTS**

1. Change in the following cardiac biomarkers: N-Terminal Prohormone of Brain Natriuretic Peptide (NT-proBNP) and soluble suppression of tumorigenicity 2 (sST2) between baseline and day 90 post initial infusion.
2. Change in RV systolic function and volumes assessed by 2D and 3D echocardiography and gated blood pool SPECT ventriculography scan between baseline and day 90 post initial infusion.
3. Hospitalizations due to right HF (as defined by INTERMACs) at day 90.
4. 6 minute walk distance changes between baseline and day 90 post initial infusion.
5. Change in Quality of life (Kansas City Cardiomyopathy Questionnaire; KCCQ) between baseline and day 90 post initial infusion.

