### 1.1 Quantitative Immune Response - biomarkers Array.

At all time points blood samples from all patients will be analyzed for the following 40 immune response biomarkers. Samples from normal donors will serve as reference.

Quantibody® Human Immune Response Biomarker Array 1 Kit (RayBiotech).

CD14	CD163	CD40	CRP	E-Selectin
------	-------	------	-----	------------

Fas (TNFRSF6/Apo-1)	Fas Ligand (TNFSF6)	GCSF	ICAM-1 (CD54)	IL-1 alpha (IL-1 F1)
IL-1 beta	IL-1 R4	IL-10	IL-12 p70	IL-13
IL-18	IL-2	IL-2 R alpha	IL-4	IL-6
IL-8	Lipocalin-2	MCP-1	MCP-2	MIF
MIP-1 alpha	MIP-1 beta	Osteopontin	PAI-1	Platelet Factor 4
Procalcitonin	RAGE	Resistin	Thrombomodulin	TNF alpha
TREM-1	Troponin I	uPAR	VCAM-1	VEGF-A

1.2. Antibody Isotype assay – Analyzing the effect of treatment with MSCs on the humoral response; levels of antibodies and isotype switch.

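### Section 9 tabulates efficacy by treatment received rather than by randomised arm, and plans no baseline-adjusted between-arm efficacy estimate; both are cheap to correct and the effect of each is modest.

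*Combined protocol and SAP*

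**What the plan says.** The grouping rule is in the opening paragraph of Section 9: "Tables will summarize all safety and efficacy outcome measures by actual treatment received". The same paragraph calls the analyses descriptive and lists what is reported: "Summary statistics will consist of sample size (N), means, standard deviations, medians, and minimum and maximum values for continuous variables", with counts and percentages for categorical variables, on available data without imputation. It says the study is deliberately unpowered, at 15 per arm, and promises a detailed SAP before data analysis. That SAP is not among the documents.

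Section 9 has no efficacy subsection. The one between-arm comparison it names is Fisher's exact test on adverse events (Section 9.2). Section 9.2 also presents safety by experimental group, which is not the term used in the opening paragraph.

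Elsewhere, efficacy is the secondary objective (Section 3.2: "To assess the efficacy of human allogeneic MSCs administered intravenously"). Allocation is 1:1, and Section 4.1 says "Enrolled subjects will be stratified by LVAD device type (HeartWare HVAD, HeartMate II or HeartMate III" (Section 9.1 agrees). Section 4.2 schedules repeated measurement: "All secondary end points will be assessed pre-MSC infusion at days 0, 30, and 60, and also at days 90, 180, and 360". The continuous efficacy endpoints there are defined as changes to Day 90. For NK cells the definition is "NK cell depletion, defined as % reduction in NK cells from baseline to day 90".

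**The concern.** Grouping by product received is usual for safety. For efficacy it gives up the comparison that randomisation protects, because whether a subject receives the assigned product can be related to how that subject is doing. Section 9 applies one rule to both.

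The second matter is what the efficacy tables will hold. The trial stratifies by device and measures every efficacy variable at baseline. Baseline enters the endpoints, since they are changes, but it is not used as a covariate, and LVAD type is not used at all. A reader of the tables can rebuild an unadjusted contrast but not an adjusted one, because that needs subject-level data. With 30 subjects, precision is the scarce resource, and an adjusted difference with its interval is a useful thing to hand to the next trial.

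**Working it through.** There is no stated power, alpha, effect size or SD to reproduce. The only arithmetic in the plan is 15 + 15 = 30, which agrees.

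**1. When do the groupings differ?** Section 5.2 rules out crossover and the study is double-blind. A subject with fewer than three infusions stays in the same group under either rule, and Section 5.2 keeps the Day-90 measurement whatever the number of infusions. That leaves two cases:

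- *Never infused.* Section 5 counts a subject as enrolled once randomised, but the treatment-received rule gives such a subject no group. Visits count from the first infusion (Section 4.2: "Baseline and days 30, 60, 90, 180, and 360 post-initial infusion"), so this subject also has no defined Day 90.
- *Wrong product.* Suppose one MSC-assigned subject receives placebo and differs from all others by D SD, with no treatment effect. By arm the difference is D/15. By product received it is −D/16. The shift is D(1/15 + 1/16) = 0.129D, or 0.06, 0.13 and 0.26 SD at D = 0.5, 1 and 2. D is assumed, and the documents give no wrong-product rate.

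**2. What can be recovered?** For a change endpoint, the planned N, mean and SD per group give the difference in means and its t-interval directly.

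**3. What does adjustment add?** Assumptions: equal SD at baseline and Day 90 (the unit below), normal data, no device effect, 15 per arm, and baseline-to-Day-90 correlation r of 0.3, 0.5 or 0.7. The documents give no r. Here c4 is the expected ratio of a sample SD to the true SD.

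- Unadjusted change score: expected width = 2 × t(28) × √(2(1−r)) × c4 × √(2/15), with t = 2.048 and c4 = 0.991.
- Adjusted: expected width = 2 × t(df) × √(1−r²) × c4 × F, where F is the mean standard-error factor over 40,000 simulated baselines. With three device strata of 5/5, df = 25, t = 2.060, c4 = 0.990 and F = 0.3725.

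| Expected 95% CI width (SD) | r = 0.3 | r = 0.5 | r = 0.7 |
|---|---|---|---|
| Change score, unadjusted | 1.754 | 1.483 | 1.148 |
| Baseline + three device types (df 25) | 1.449 | 1.316 | 1.085 |
| Narrower by | 17.4% | 11.3% | 5.5% |
| Baseline + two device types, 5/5 and 10/10 (df 26) | 1.446 | 1.313 | 1.083 |
| Baseline + sparse mix 1/0, 4/4, 10/11 (df 25) | 1.475 | 1.339 | 1.104 |
| Baseline only (df 27) | 1.442 | 1.309 | 1.080 |

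The last row shows that the whole gain is from baseline. Under these assumptions, device terms only cost a little.

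An unadjusted change score would need about 43, 38 and 33 subjects to match the three-device adjusted width. With 12 per arm at Day 90 (15 less the 20% mortality expected in Section 4.2, assumed equal by arm and all before Day 90), the widths are 1.981/1.674/1.297 unadjusted and 1.652/1.500/1.236 adjusted, which is 17%, 10% and 5% narrower.

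**4. How many intervals?** Section 7.1 says "blood samples from all patients will be analyzed for the following 40 immune response biomarkers". With NK cells that is 41 secondary markers. With no effect anywhere, 41 × 0.05 = 2.05 intervals would be expected to exclude zero. If the markers were independent, the chance of at least one is 1 − 0.95^41 = 0.88.

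**5. NK scale.** As a percentage reduction, a halving scores +50 and a doubling −100. If the median ratio is 1 and the log ratio is normal with SD 0.3, 0.5 or 0.7 (assumed), the mean percentage reduction is 100 × (1 − exp(s²/2)) = −5%, −13% or −28%. The median stays at 0.

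**The case against.** The strongest reply is that the descriptive plan is deliberate. The study is exploratory, safety is the primary objective, and the sponsor says openly that it is unpowered. A detailed SAP is still to come. Blinding without crossover makes the grouping rule nearly harmless, and the planned statistics already yield an unadjusted difference and interval. Dozens of unadjusted intervals also invite over-reading.

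Much of this stands. No hypothesis test is needed. The grouping effect is small, and the multiplicity cost is real. Two things are not answered. Section 9 does not leave efficacy grouping open but sets it. And descriptive intent does not explain why adverse events get a between-arm comparison while efficacy gets no contrast.

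Several stronger readings are tempting, and the documents do not support them:

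- *That the efficacy results will be materially biased.* This needs wrong-product subjects, and nothing in the documents suggests there will be any number of them.
- *That arms cannot be compared, or that baseline is ignored.* The unadjusted contrast is recoverable, and baseline is built into the change endpoints. It is missing only as a covariate.
- *That adjusting for LVAD type buys precision.* The calculation assumes no device effect and shows no gain. The reason to include it is that it is the stratification factor.
- *That the NK endpoint is unsound.* Section 9 also plans the median, which would show the skew. With no treatment effect and equal spread, the distortion of the mean cancels between arms.
- *That the final analysis will lack these items.* The point is established for Section 9 as written; the future SAP could supply them.

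**Conclusion.** The point holds in a limited form. Section 9 groups efficacy by treatment received in a randomised trial. That is the wrong default but probably of little consequence: about 0.13 SD per wrong-product subject lying 1 SD from the rest. It also plans no adjusted between-arm efficacy estimate. The loss is an interval about 17%, 11% or 5.5% narrower than for the unadjusted change score, at assumed correlations of 0.3, 0.5 and 0.7.

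The size depends on those correlations and on the comparator. Against an unadjusted comparison of Day-90 values (width 1.483 SD at any r), adjustment would give an interval 2%, 11% and 27% narrower (1 − 1.449/1.483, 1 − 1.316/1.483, 1 − 1.085/1.483). Severity is minor for the grouping alone, and minor to should-fix with the missing adjusted estimate.

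**What to change.** In Section 9, carried into the SAP:

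1. Summarise efficacy by randomised arm for all randomised subjects with available data. Keep treatment received for safety, and use that same term in Section 9.2.
2. For continuous Day-90 efficacy measures, add the MSC-minus-placebo difference with a 95% CI from a model with baseline value and LVAD type as covariates. Pool sparse device types by a rule fixed before unblinding. Label the estimates exploratory, and state that the intervals are not tests and that about 2 of 41 would exclude zero by chance.
3. Optionally, report NK cells also as a geometric-mean ratio, alongside the percentage reduction defined in Section 4.2 and not in place of it.

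The cost is a few sentences and table columns in a SAP not yet written, with no new subjects, visits or data. The model uses 3 more degrees of freedom than an unadjusted comparison (28 to 25), or 2 if device is pooled to two levels (28 to 26). The real downside is the risk that many exploratory intervals are over-read, which the labelling in item 2 is there to limit.

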### **9.1 Randomization**

Once eligibility and consent are confirmed, participants will be randomly assigned to the experimental or placebo group in a 1:1 allocation ratio, stratified by LVAD type.

### **9.2 Primary Safety Analysis**

All safety outcomes will be summarized in tables and listings presented by experimental group. Continuous measures will be summarized with descriptive statistics (N, mean, SD, median, min, max). Categorical measures will be summarized using counts and percentages. The incidence of AEs will be presented by

toxicity grade, MedDRA system organ class and preferred term, and by relationship of the AEs to the study treatment and compared using a Fisher's Exact Test. Laboratory and vital signs data will be presented using shift tables and summaries of change from baseline to next infusion or follow up visit.

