#### **5.4 Study Termination**

The Sponsor has the right to terminate the study at any time. Reasons for terminating the study may include, but are not limited to, the following:

- The incidence or severity of AEs in this or other studies indicates a potential health hazard to subjects.
- Unsatisfactory subject enrollment.
- Rate of enrollment of < one subject per 3 months.
- An excess drop out of subjects (a total of  $\geq 5$  subjects per each arm, but not due to VAD –related mortality).
- Inaccurate or incomplete data recording.
  - $\geq 20\%$  missing data for the primary safety endpoints.
  - $\geq 30\%$  missing data for the efficacy endpoints.

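### Section 9.2 reports day-360 mortality as a crude percentage with no denominator rule for subjects who leave early; a Kaplan-Meier estimate beside the counts is a cheap improvement

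*Combined protocol and SAP*

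**What the plan says.** Section 4.2 lists the primary safety items, with assessments from baseline to day 360. They include uncontrolled systemic infection, unstable arrhythmia and "All-cause mortality. This will be reviewed by the DSMB". The same item gives survival of LVAD patients as 95% at 1 month, 81% at 1 year and 70% at 2 years, and expects 20% mortality in the study.

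Section 9.2 covers all safety outcomes. It does not name mortality separately. Its method is "Categorical measures will be summarized using counts and percentages", with adverse event incidence "compared using a Fisher's Exact Test". Section 9 adds "No substitutions will be made for missing data. All analyses will be based on available data" and "Summary tables will indicate the number of subjects with complete data for each measurement, event or outcome".

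Three other sections bear on early exit:
- Section 5.3 lets subjects withdraw at any time and lets the investigator discontinue them. One early-termination examination is attempted.
- Section 8.2.1 ends general event reporting at completion or discontinuation. After that, only SAEs attributed to study treatment are reported.
- Section 5.4 names "An excess drop out of subjects", put at 5 or more per arm, as one possible reason to stop the study.

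The documents contain no Kaplan-Meier, cumulative-incidence, person-time or censoring rule, and no definition of when a subject who left early is available for an event. A detailed SAP is promised before data analysis; it is not part of the documents.

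**The concern.** Someone who leaves alive at day 100 has been observed for part of the year only. A percentage has to put that person somewhere. Keeping them in the denominator treats them as a survivor to day 360. Dropping them for incomplete data removes a survivor while every observed death stays in. The first choice understates the day-360 risk and the second overstates it, and the plan does not choose between them. Section 8.2.1, read subject by subject, adds to the problem, because an unrelated death after withdrawal might never be recorded.

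Two uses of the figure are at stake. One is the comparison of arms, which is distorted if the arms lose different numbers. The other is the comparison with the survival benchmarks in Section 4.2, which are tied to fixed time points and so are not matched by a percentage based on partial follow-up.

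**Working it through.** **Plan's own figure.** One-year mortality from the Section 4.2 survival figures is 1 − 0.81 = 19%, close to the stated 20%. Enrolment opens only after discharge and stabilisation (Subject Participation, under Section 4), so some early deaths have already happened. Conditional on surviving the first month:
- Months 1 to 12: 1 − 0.81/0.95 = 14.7%.
- Months 1 to 13: S(13) = 0.81 × (0.70/0.81)^(1/12) = 0.800 by log-linear interpolation, so 1 − 0.800/0.95 = 15.8%.

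I therefore use 15% and 20% as the range for the true risk.

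**Assumptions.** 15 per arm (Section 9). Constant death hazard over the 360 days. Withdrawal at a constant hazard, independent of outcome. No drop-out rate is stated, so I take an expected k = 1 to 5 of 15 leaving alive.

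**Formulae.** With true risk p, the death hazard is λ = −ln(1 − p). The withdrawal hazard m solves m/(λ+m) × [1 − exp(−(λ+m))] = k/15. The observed death proportion is D = λ/(λ+m) × [1 − exp(−(λ+m))]. Deaths over all subjects has expectation D; deaths over complete-data subjects is D/(1 − k/15).

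**Example, p = 20%, k = 4.** λ = 0.2231 and m = 0.3505, so λ+m = 0.5736 and 1 − exp(−0.5736) = 0.4365. D = 0.2231/0.5736 × 0.4365 = 17.0%. Over complete data: 0.170/(11/15) = 23.2%.

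| Leaving, of 15 | True 20%: deaths/15 | True 20%: complete data | True 15%: deaths/15 | True 15%: complete data |
|---|---|---|---|---|
| 1 | 19.3% | 20.7% | 14.5% | 15.5% |
| 2 | 18.5% | 21.4% | 13.9% | 16.1% |
| 3 | 17.8% | 22.2% | 13.4% | 16.7% |
| 4 | 17.0% | 23.2% | 12.8% | 17.4% |
| 5 | 16.2% | 24.3% | 12.2% | 18.3% |

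The bias runs from −0.7 to −3.8 or +0.7 to +4.3 points at 20%, and from −0.5 to −2.8 or +0.5 to +3.3 points at 15%. In 40,000 simulated arms of 15 with p = 20% and k = 4, Kaplan-Meier averaged 20.0%.

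**Second model.** Take h = −ln 0.81 = 0.2107 and withdrawal times spread evenly, with probability d of falling within the year. Observed deaths = 0.19 − d × 0.0917, where 0.0917 is the integral of h·t·exp(−ht) over the year; known survivors = 0.81 × (1 − d). For d = 5/15 this gives 15.9% over all and 0.1594/(0.1594 + 0.54) = 22.8% over complete data. For d = 3/15 it gives 17.2% and 20.9%. The truth is 19.0%, so the pattern is the same.

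**Unequal loss.** If both arms have a true 20% risk and 1 versus 4 leave, the percentages are 19.3% versus 17.0% over all (gap 2.3 points) or 20.7% versus 23.2% over complete data (gap 2.5 points, in the opposite direction).

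**One concrete arm.** Assume deaths at days 60, 150 and 300 and withdrawals at days 45, 100, 200 and 250. The numbers at risk at the deaths are 14, 12 and 9. Kaplan-Meier gives 1 − (13/14)(11/12)(8/9) = 24.3%, against 3/15 = 20.0% or 3/11 = 27.3%.

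**Scale.** One death in 15 is 6.7 points. The largest bias in the table, 4.3 points, is 0.043 × 15 = 0.65 of a death. In the simulation the standard deviation of an arm's estimate was about 10 to 13 points, depending on the estimator. Exact 95% intervals are 4.3% to 48.1% for 3/15 and 6.0% to 61.0% for 3/11.

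**The case against.** The study is unpowered and its analyses are declared descriptive. Listings and numbers with complete data are promised, the DSMB reviews mortality, and about three deaths per arm can be read one by one. A missed or stopped infusion does not by itself end follow-up (Section 5.2 and the infusion section). The SAP could still settle the method. These points limit the importance of the finding but do not remove it. Kaplan-Meier is itself descriptive, and nothing in the documents commits the SAP to a time-based estimate.

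A reader might infer more than the documents support:
- **That an arm difference of 3 to 4 points is to be expected.** It needs 5 leaving one arm and none leaving the other. Five per arm in Section 5.4 is a possible reason to stop the study, not a forecast.
- **That the plan has chosen the complete-data denominator.** Section 9 says that number will be shown. It does not say it is the divisor for events.
- **That the needed dates are already collected.** Section 8.2.2 records event start and end dates and Section 5.3 the reason for withdrawal. No last-known-alive date is mentioned.

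Two technical objections also stand. Kaplan-Meier is unbiased only if leaving is unrelated to prognosis, and Section 5.3 allows discontinuation for medical reasons. For infection and arrhythmia, death is a competing event, and subjects without an ICD are monitored for arrhythmia only in 7-day periods (Section 7.1), so a simple time-to-first-event curve would not be right for them.

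**Conclusion.** The point holds at modest size. The stated summary has no denominator rule, and either natural choice is biased for day-360 mortality once anyone leaves early. With 1 to 5 of 15 leaving non-informatively, the bias is about 1 to 4 points on a 15% to 20% risk, less than one death per arm and below sampling error. These figures rest on an assumed drop-out range, constant hazards and independent withdrawal. With complete follow-up the crude percentage is correct. The tempting conclusion that the primary safety analysis is invalid is not supported: the raw counts remain true and the study claims no powered comparison. The change is worth making because it costs little, settles the denominator before data are seen, and puts an interval beside a percentage that would otherwise be printed bare.

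**What to change.** In Section 9.2 and the SAP:

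1. Report all-cause mortality per arm by Kaplan-Meier from first infusion, with 95% confidence intervals at days 90, 180 and 360, censored at the last date known alive. Print raw counts over all treated subjects beside it.
2. Make sure the CRF records the last-known-alive date. After withdrawal, seek vital status to day 360 where consent allows, because this reduces reliance on non-informative censoring.
3. For systemic infection, unstable arrhythmia and SAEs, add events per patient-month at risk with exact confidence intervals. If time to first event is shown, use cumulative incidence with death as a competing event. State that arrhythmia in subjects without an ICD is observed only during monitoring periods.

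The cost is a few sentences, a little extra analysis, one date field, and a vital-status enquiry for subjects who withdraw.

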### **9.3 Determination of Sample Size**

This Study is exploratory and its sample size is not determined by statistical power considerations, but is considered appropriate for an early phase safety trial.

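### Adverse event incidence is compared by Fisher's exact test at 15 per arm, with no alpha, nominal label or interval, in a plan that calls itself descriptive and unpowered

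*Combined protocol and SAP*

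**What the plan says.** Safety is the only primary objective (Section 3.1) and is the primary endpoint (Section 4.2). Section 9 opens with "Statistical analyses will be descriptive" and adds "This study intentionally is not powered and will enrolled 30 patients with 15 in each of the two randomization arms". Section 9.3 repeats that "its sample size is not determined by statistical power considerations".

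Section 9.2 is mostly in keeping with that: tables, listings, counts and percentages, shift tables and summaries of change. One clause differs. It breaks AE incidence down four ways, namely by grade, system organ class, preferred term and relationship, and says that the two arms will be "compared using a Fisher's Exact Test". This is the only between-arm test named in Section 9. The section gives no alpha, sidedness, multiplicity rule, confidence interval or rule for reading the p-values. Section 9 defers detail to a Statistical Analysis Plan to be written before the data are analysed.

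**The concern.** A family of significance tests, one per AE category, does not fit easily in a plan described as descriptive. With 15 per arm, most of those p-values will be non-significant even if the product causes a moderate excess of events. The p-value alone does not show how large an excess the data leave open, and that is the main question in a small trial whose primary objective is safety. In the other direction, an isolated significant category would have no pre-stated interpretation. What is at stake is how the primary result is reported. Participant protection during the trial rests with the Data Safety and Monitoring Board (DSMB), the investigator and the sponsor.

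**Working it through.** **Inputs from the protocol.** 15 per arm (Section 9); 1:1 allocation (Section 9.1); Fisher's exact test on AE incidence (Section 9.2). The only anticipated event rate is for death, in Section 4.2: "we would expect a 20% mortality rate in our patient population".

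**Assumptions.** Alpha and sidedness are not stated, so two-sided 0.05 is used. AE rates are not stated, so a range is shown. The plan gives no power or detectable difference, so there is no figure of its own to reproduce.

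**Step 1: splits that reach p ≤ 0.05.** For a events on active and b on placebo, the table probability is C(15,a)·C(15,b)/C(30,a+b). The two-sided p-value sums all tables with the same margins that are no more probable.

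- 5 vs 0: 2 × C(15,5)/C(30,5) = 2 × 3003/142506 = 0.042.
- 4 vs 0: 2 × C(15,4)/C(30,4) = 2 × 1365/27405 = 0.0996.
- The smallest significant active-arm counts against 1, 2 and 3 placebo events are 7 (p = 0.035), 9 (p = 0.021) and 10 (p = 0.025).

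**Step 2: power.** Sum Bin(a; 15, p₁) × Bin(b; 15, p₀) over those of the 16 × 16 outcomes with p ≤ 0.05.

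| Placebo vs active | Power, two-sided 0.05 |
|---|---|
| 10% vs 20% | 4.1% |
| 20% vs 40% | 11.2% |
| 10% vs 30% | 14.9% |
| 20% vs 50% | 24.6% |
| 0% vs 30% | 48.5% |
| 0% vs 40% | 78.3% |
| 0% vs 50% | 94.1% |

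With no placebo events the test needs at least 5 of 15 on active, so the 0% vs 40% figure is P(Bin(15, 0.4) ≥ 5) = 0.783.

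Sensitivity: at one-sided 0.05, power is 19.1% for 20% vs 40% and 25.6% for 10% vs 30%. With 12 per arm (an assumed 20% loss), 20% vs 40% falls to 9.2% two-sided.

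**Step 3: true size and multiplicity.** Setting p₁ = p₀ gives a true size of 0.55% at a 10% rate, 1.67% at 20%, 1.77% at 25% and 1.70% at 30%. At a 5% rate it is 0.06%. For an illustrative 50 independent categories, the chance of at least one false signal is 1 − (1 − size)^50: about 3% at a 5% event rate, 24% at 10% and 57% at 20%.

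**Step 4: what intervals would show.** The Clopper-Pearson 95% upper limit for 0/15 is 1 − 0.025^(1/15) = 21.8%. For 3/15 the interval is 4.3% to 48.1%.

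As an example, take a 20% background rate that doubles. The expected split is 15 × 0.20 = 3 on placebo and 15 × 0.40 = 6 on active. Fisher gives p = 0.43. The 95% Newcombe interval for the risk difference is −12 to +47 percentage points. The interval shows that a large excess is not excluded; the p-value does not.

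**The case against.** The strongest reply is that the protocol hides nothing. It says openly that the study is unpowered and exploratory, and no hypothesis, success criterion or stopping decision depends on a Fisher p-value. The DSMB reviews accumulating safety data and can recommend suspending enrollment without any test (Section 8.5), and Section 4.2 sends mortality to it. The Fisher clause covers AE incidence only; laboratory values, vital signs and the rest are summarised descriptively. Unadjusted p-values beside AE counts can themselves be read as descriptive. All of this stands.

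Four stronger readings are tempting and are not supported.

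- A reader might infer that the test can hardly detect harm at all. Step 2 shows otherwise for very large effects, especially for events absent on placebo.
- A reader might infer that the trial intends to treat non-significance as proof of safety. Nothing in Sections 9 to 9.4 says so; the text is silent.
- A reader might infer serious false-positive inflation across categories. The test is so conservative here that this matters mainly for common events.
- A reader might infer that intervals are ruled out. Section 9 promises a detailed analysis plan that could add them; their absence can be asserted only of this document.

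What the reply does not answer is that Section 9.2, carried forward as written, gives an unlabelled p-value as the only between-arm comparison of AE incidence. DSMB oversight during the trial does not settle how the final result is reported.

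**Conclusion.** The point holds as a cheap improvement in analysis and wording. The Fisher clause and the descriptive, unpowered framing should be reconciled. For excesses of 20 to 30 points over a 10% or 20% background, power is 11% to 25%, so a non-significant result carries little information about safety. For an event absent on placebo, power reaches 78% at a 40% active rate and 94% at 50%. At common rates of 10% to 30%, the true size is about 0.55% to 1.8%.

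The power and size figures rest on two-sided 0.05, 15 evaluable subjects per arm and the assumed event rates; the last two come from the range shown because the plan gives no AE rates. The one-sample limits (21.8% for 0/15; 4.3% to 48.1% for 3/15) do not depend on an assumed rate or on the choice of test.

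**What to change.** In Section 9.2, and in the detailed analysis plan when it is written:

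1. Report per-arm incidence with exact (Clopper-Pearson) 95% confidence intervals, and the risk difference with an exact or score 95% interval, for all-cause death, any SAE, any related AE, infusion reactions and each system organ class.
2. State that the safety conclusion rests on these estimates and intervals.
3. If Fisher p-values are kept, label them nominal and descriptive, give their sidedness, and state that non-significance will not be read as evidence of safety. Deleting the test is optional; the label is enough.

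No extra subjects, visits or data are needed, because the intervals come from counts that Section 9.2 already tabulates. The cost is extra table columns and a short edit to the text. The downside is that the intervals will be wide and will look less favourable than a column of non-significant p-values.
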